8.1.3 Unanticipated Problem

An unanticipated problem (UP) is any incident, experience or outcome involving risks to subjects or others in any human subjects research that meets all of the following criteria:

- Unexpected (in terms of nature, severity or frequency) given (a) the research procedures that are described in the IRB-approval protocol and informed consent document, and (b) the characteristics of the subject population being studied;
- Related or possibly related to participation in such research (e.g., there is a reasonable possibility that the incident, experience or outcome may have been caused by the procedures involved in such research); and
- Suggests that the research places subjects or others at a greater risk of harm (including physical, psychological, economic or social harm) than was previously known or recognized.

8.2 Adverse Event Reporting Period

The study period during which adverse events must be reported is normally defined as the period from the initiation of any study procedures (e.g., after the first dose of study treatment) to the end of the study treatment (e.g., last dose of study treatment) and/or follow-up. For this study, the study treatment follow-up is defined as 30 days following the last administration of study treatment, or 30 days following the decision to remove the subject from study treatment, whichever is earliest.

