2.2 Secondary Objectives & Endpoints

*Note: The secondary objects only apply for patients who are initiated on treatment with an OncoTreat-prioritized FDA-approved or early-phase investigational drug.

2.2.1 Objectives:

The secondary objectives of this study are to:

- To describe the safety and tolerability of using OncoTreat to inform rational treatment decision in subjects with advanced PDA who have progressed on one or two prior lines of therapy.
- To assess the efficacy of OncoTreat by estimating the disease control rate (DCR) at 16 and 24 weeks, the median progression-free survival (PFS), the overall survival (OS), and the CA 19-9 tumor marker response.
- To assess the pharmacokinetics of each OncoTreat-prioritized agent in subjects with advanced PDA.

2.2.2 Endpoints:

Secondary endpoints of interest include:

- Safety/tolerability
 - Incidence of Grade 3/4 adverse events (AEs) in terms categorized and graded according to the National Cancer Institute Terminology Criteria for Adverse Events (NCI CTCAE v4.0).
 - Incidence of dose modifications, interruptions, and discontinuations.
 - Note: OncoTreat-prioritized agents will be dosed at the FDA-approved dose (if available) or the recommended phase 2 dose for investigational agents. Safety endpoints as they pertain to specific drugs will not be assessed in this prospective study, as only a very small number of patients will be assigned to any one of these drugs, all of which are FDAapproved or have been studied in early phase clinical trials and have track records of safety/tolerability.
- DCR, defined as the proportion of subjects with a complete or a partial response as the best response or stable disease, according to RECIST v1.1 criteria.
- PFS, defined as the time from first dose of OncoTreat-prioritized drug to the first occurrence of disease progression or death from any cause (whichever occurs first), using RECIST v1.1 criteria.
- OS, defined as the time from first dose of OncoTreat-informed study drug to death due to any cause.
- Tumor marker response of CA 19-9, defined as ≥ 50% in CA 19-9 in relation to the baseline level at least once during the treatment period.
- Serum concentration or PK parameters for each OncoTreat-prioritized agent.
- Relationship between serum concentration or PK parameters and endpoints of interest.

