consideration. If an OncoTreat-informed drug is identified and treatment is recommended by the PMTB, the subject may proceed with consent for Part 2.

The PMTB will convene at CUMC on a monthly or as needed basis. A quorum of at least 5 members, including the principal investigator, one additional medical oncologist and one non-Columbia individual, must be present for each meeting. Teleconference is permitted if a PMTB member is located off campus.

(5) If the PMTB recommends a FDA-approved or investigational oncology drug, and the drug is available, the subject will consent to Part 2 and begin the study agent at the time of disease progression or intolerance to therapy. A pre-study treatment biopsy will be required to confirm that the MR dependencies of the subject's tumor have not changed over time or in response to first-line therapy (a theoretical concept that needs to be formally assessed).

If no FDA-approved or investigational agents are identified at the time of first disease progression or intolerance to first-line therapy, or the OncoTreat-prioritized drug is not available in a time manner for administration, the subject will continue on to physician's choice second-line treatment (chemotherapy or clinical trial). The subject will be followed for response evaluation. At the time of second disease progression or intolerance to treatment, the subject will be re-evaluated for enrollment on Part 2. If a FDA-approved or investigational agent is identified, and the drug is available, the subject may consent to Part 2 and begin the study agent following a pre-study treatment biopsy. If no FDA-approved or investigational agents are identified, or the OncoTreat-prioritized drug is not available, the subject will screen fail for Part 2 and will be followed for response evaluation.

(6) The dosing and schedule of the OncoTreat-prioritized drug will be described in the subprotocol for each agent. For each of the FDA-approved drugs, the dose and dosing schedule will be aligned with the currently approved dose and schedule in the product U.S. Package Insert (USPI) and Investigator's Brochures (IBs). For the investigational agents, the dose and dosing schedule will be aligned with the current recommend phase 2 dose (R2PD).

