8.5.2 SAE Reporting to Incyte

The Principal Investigator (PI) must report all Serious Adverse Events (SAEs) to Incyte within 24 hours of learning of an event, regardless of the PIs causality assessment. This notification should be provided on a completed Serious Adverse Event (SAE) form. SAE reporting for each subject begins the day the informed consent is signed by the patient and within 30 days after subject has completed or discontinued from the study or has taken last dose of the study drug, or as described in the protocol.

SAEs, occurring using Incyte Study drug, are reported in accordance with the effective protocol. SAEs occurring with any other commercial drug are reported to the manufacturer of that drug in accordance with regulations and protocol.

Initial SAEs and/or subsequent follow-up reports should be reported via email to [contact] or fax [name]. SAE reports should be for a single subject. SAE forms should be sent with a cover sheet and any additional attachments.

All adverse event information is reported to Incyte on the Principal

Investigator's/Institution's Adverse Event Report Form, or a CIOMS-I or MedWatch Form FDA 3500A, or on an Adverse Event Report Form which may be provided by Incyte upon request. The Principal Investigator does not provide medical records (e.g., discharge summary) to Incyte, unless specifically requested.

8.5.2 8.5.3 FDA Notification by Sponsor-Investigator

The Columbia University Medical Center Sponsor-Investigator, as holder of the IND, will be responsible for all communication with the FDA. Columbia University Medical Center Principal Investigator will report to the FDA, regardless of the site of occurrence, any adverse event that is serious, unexpected and there is evidence to suggest a causal relationship between the drug and the adverse event. These must be reported to the FDA and any affiliate sites as soon as possible, but in no case later than 15 calendar days after the sponsor determines that the information qualifies for reporting. The Sponsor-Investigator will also submit an IND annual report to the FDA in accordance with 21.CFR 312.33.

The Columbia University Medical Center Sponsor Investigator must report to the FDA and any affiliate site investigators as follows:

- Any unexpected fatal or life-threatening event must be reported as soon as possible, but no later than 7 calendar days after the sponsor investigator initial receipt of the information

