10.2 Definitions

Evaluable for toxicity: All patients will be evaluable for toxicity from the time of their first treatment with an OncoTreat-prioritized agent.

Evaluable for objective response: Only those patients who have measurable disease present at baseline, have received at least one cycle of therapy, and have had their disease re-evaluated will be considered evaluable for response. These patients will have their response classified according to the definitions stated below. (*Note*: Patients who exhibit objective disease progression prior to the end of cycle 1 will also be considered evaluable.)

Evaluable for feasibility – primary outcome: All subjects who receive a single dose of study drug will be included in the primary outcome analysis of feasibility.

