10.7.5 Safety Endpoints

The safety analysis will be based on subjects who experienced toxicities as defined by CTCAE criteria. Safety will be assessed by quantifying the toxicities and grades experienced by subjects who have received the study drug, including serious adverse events (SAEs) and events of clinical interest (ECIs).

Safety will be assessed by reported adverse experiences using CTCAE, Version 4.0. The attribution to study treatment, time-of-onset, duration of the event, its resolution, and any concomitant medications administered will be recorded. AEs will be analyzed including but not limited to all AEs, SAEs, fatal AEs, and laboratory changes.

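### The Part 2 safety result starts at first dose and covers dosed subjects only, so harms from the mandatory pre-dose biopsy fall outside it, and the sections disagree on when adverse event collection begins

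*Combined protocol and SAP*

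**What the plan says.** The secondary safety objective in Section 2.2 is "To describe the safety and tolerability of using OncoTreat to inform rational treatment decision in subjects with advanced PDA". A note in the same section adds that drug-specific safety endpoints will not be assessed, so the pooled, strategy-level description is the trial's main safety result.

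Three places define what enters that result:

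- Section 2.2, opening note: "The secondary objects only apply for patients who are initiated on treatment".
- Section 10.2: "All patients will be evaluable for toxicity from the time of their first treatment with an OncoTreat-prioritized agent".
- Section 10.7.5: "Safety will be assessed by quantifying the toxicities and grades experienced by subjects who have received the study drug".

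Section 4.1, in the step on Part 2 entry, says: "A pre-study treatment biopsy will be required to confirm that the MR dependencies" of the tumor are unchanged. Section 4.4 and note j to Table 6 also make this biopsy a condition that precedes study drug.

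On collection, Section 8.2 runs the reporting period "from the initiation of any study procedures (e.g., after the first dose of study treatment". Section 8.5.2, on reports to one manufacturer, says: "SAE reporting for each subject begins the day the informed consent is signed by the patient". Tables 6 to 9 mark adverse event review at screening. Section 8.2.2 files clinically significant screening abnormalities as pre-existing conditions. Section 9.4.2 files screening examination findings as medical history and treats new findings as adverse events only after the first dose.

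**The concern.** The repeat biopsy is there to confirm the OncoTreat profile, so it is an invasive part of the strategy whose safety is to be described. It lies between Part 2 consent and first dose, which is the interval that the analysis definitions leave out.

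The omission need not be neutral. A biopsy complication can itself stop a subject from being dosed. An infection needing systemic therapy is an exclusion in Section 5.2. A bleed could breach the hemoglobin criterion in Table 5 of Section 5.1. A fall in performance status could show at the check within 3 days before dosing (Table 6, note m). Such a subject leaves both the numerator and the denominator, so the described risk of the strategy would tend to be too low.

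The conflicting collection rules add a second problem. The same post-biopsy finding could be logged as an adverse event, a pre-existing condition or medical history, depending on which section the site follows.

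**Working it through.** No published figure is in dispute, so the check is a comparison of the definitions followed by an illustration of scale.

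**Step 1. Definitions side by side.**

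| Section | Governs | Subjects | Start |
|---|---|---|---|
| 2.2 note | secondary objectives, including safety | started on drug | none stated |
| 10.2 | toxicity evaluation | all treated | first treatment |
| 10.7.5 | safety analysis | received drug | none stated |
| 8.2 | adverse event reporting | not limited | any study procedure, with first dose as the example |
| 8.5.2 | serious events to one manufacturer | each subject | consent |
| 8.5.4 | serious events to the monitoring committee | not limited | none stated |
| Tables 6–9 | adverse event review | not limited | screening |
| 8.2.2, 9.4.2 | examination findings | not limited | screening findings are baseline; under 9.4.2, adverse events after first dose |

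**Step 2. Apply them to three cases.**

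- *Biopsied, never dosed.* Outside the safety result under 2.2, 10.2 and 10.7.5 alike.
- *Event after the biopsy but before the first dose, subject dosed later.* The subject is in the safety set. The event is not counted under 10.2. Section 10.7.5 sets no start date, so this loss rests on 10.2 alone.
- *Event after an optional on-treatment or end-of-treatment biopsy.* These biopsies follow first dose (Table 6, note k), so they fall inside the toxicity window. There is no gap.

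**Step 3. Numbers of subjects.** Section 12 expects matches in 50% of 30 and treatment in 30% of 30:

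- matched: 30 × 0.50 = 15
- treated: 30 × 0.30 = 9 (and 15 × 0.60 = 9)
- matched, not treated: 15 − 9 = 6

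The documents do not say how many of those 6 would have had the Part 2 biopsy. If between 9 and 15 are biopsied (assumption), 0 to 6 of them lie outside the safety set, which is 0/9 = 0% to 6/15 = 40%.

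**Step 4. Chance that at least one pre-dose complication occurs.** With complication rate r per biopsy (assumption) and n biopsied, this is 1 − (1 − r)^n:

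| r | n = 9 | n = 15 |
|---|---|---|
| 1% | 1 − 0.99^9 = 8.6% | 1 − 0.99^15 = 14.0% |
| 2% | 1 − 0.98^9 = 16.6% | 1 − 0.98^15 = 26.1% |
| 5% | 1 − 0.95^9 = 37.0% | 1 − 0.95^15 = 53.7% |

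With 9 treated subjects, one subject is 1/9 = 11.1% of the denominator, so a single event counted or not counted visibly changes an incidence.

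**The case against.** The strongest reply is that the dosed-only scope is declared, not accidental. Section 2.2 states it, and several listed endpoints (dose modifications, interruptions, discontinuations) can arise only in a dosed subject. That stands as a reason to leave the on-drug analysis alone. It does not answer why a mandatory step of the strategy has no place in any safety table when the objective is worded at strategy level.

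A reader might also infer more than the documents support:

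- *That Section 8.2 sets a first-dose window.* It does not. Its main wording would include the biopsy, and only the example points to first dose. The defect there is a contradiction. The first-dose count comes from Section 10.2.
- *That pre-dose harms go unrecorded.* Some would be captured: by screening review, by serious event reports to the one manufacturer (8.5.2) and to the monitoring committee (8.5.4), and by the unanticipated-problem rules (8.1.3, 8.5.1). The adverse event definition in 8.1.1 is also broad. What is missing is a rule that carries these records into a safety endpoint.
- *That all biopsy harms drop out.* Only the required pre-dose biopsy is affected.
- *That the percentages are the chance of an omission, or a bias.* They are the chance that a complication occurs, at assumed rates and assumed biopsy counts. The 9 and 15 are expected treated and matched subjects, not numbers biopsied.

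The diagnostic biopsy at first presentation belongs to Part 1, a separate protocol, and is not part of this point.

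**Conclusion.** The point holds at the level of the safety result. Subjects biopsied for Part 2 and never dosed are excluded by three concordant statements. Pre-dose events in subjects dosed later are not counted under Section 10.2. The collection rules give at least three different starts: consent, screening or any study procedure, and first dose.

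The likely direction is an understated procedural risk, because a complication that prevents dosing removes the subject. The size cannot be estimated from the documents. The illustration (9% to 37% with 9 biopsied, 14% to 54% with 15, at rates of 1% to 5%) shows only that at least one such event in this trial is plausible under those assumptions. Neither co-primary endpoint definition nor the on-drug toxicity analysis is affected, so this is a gap in a secondary objective that should be closed before data are analyzed.

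**What to change.** 1. In Section 8.2, delete the parenthetical example of first dose and state one start of adverse event collection, Part 2 consent, for all study drugs. Say in 8.5.2 that the same start applies to serious events whichever drug is assigned.
2. In Sections 8.2.2 and 9.4.2, separate conditions already present at Part 2 consent (baseline history) from findings that arise afterwards, including after the biopsy (adverse events).
3. In Section 10.2, keep the present definition for on-drug toxicity and add a second set: all subjects who undergo the required Part 2 biopsy. Amend the note in Section 2.2 and the population in Section 10.7.5 so that they do not exclude it.
4. Report procedure-related adverse events and serious adverse events in that second set in their own table, with the number biopsied and the number never dosed. Do not merge it with the on-drug incidence.

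The cost is wording changes in seven sections (2.2, 8.2, 8.2.2, 8.5.2, 9.4.2, 10.2, 10.7.5) and one small table. Adverse event review at screening is already scheduled, so no visit or procedure is added, and the on-drug results do not change.

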8.2.1 Baseline/Prexisting Condition

A baseline/preexisting condition is one that is present at the start of the study. A preexisting condition should be recorded as an adverse event if the frequency, intensity, or if the character of the condition worsens during the study period.

8.2.2 General Physical Examination Findings

At screening, any clinically significant abnormality should be recorded as a preexisting condition. At the end of the study, any new clinically significant findings/abnormalities that meet the definition of an adverse event must also be recorded and documented as an adverse event.

8.2.3 **Post-Study Adverse Event**

All unresolved adverse events should be followed by the investigator until the events are resolved, the subject is lost to follow-up, or the adverse event is otherwise explained. At the last scheduled visit, the investigator should instruct each subject to report any subsequent event(s) that the subject, or the subject's personal physician, believes might reasonably be related to participation in this study.

8.2.4 Abnormal Laboratory Values

A clinical laboratory abnormality should be documented as an adverse event if any one of the following conditions is met:

- The laboratory abnormality is not otherwise refuted by a repeat test to confirm the abnormality.
- The abnormality suggests a disease and/or organ toxicity
- The abnormality is of a degree that requires active management (e.g., change of dose, discontinuation of the drug, more frequent follow-up assessments, further diagnostic investigation, etc).

8.2.5 Hospitalization, Prolonged Hospitalization, or Surgery

Any adverse event that results in hospitalization or prolonged hospitalization should be documented and reported as a serious adverse event unless specifically instructed otherwise in this protocol. Any condition responsible for surgery should be documented as an adverse event if the condition meets the criteria for an adverse event.

Neither the condition, hospitalization, prolonged hospitalization, nor surgery are reported as an adverse event in the following circumstances:

- Hospitalization or prolonged hospitalization for diagnostic or elective surgical procedures for a preexisting condition. Surgery should **not** be reported as an outcome of an adverse event if the purpose of the surgery was elective or diagnostic and the outcome was uneventful.
- Hospitalization or prolonged hospitalization required to allow efficacy measurement for the study.
- Hospitalization or prolonged hospitalization for therapy of the target disease of the study, unless it is a worsening or increase in frequency of hospital admissions as judged by the clinical investigator.

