- If a severe non-hematologic adverse reaction develops (such as severe hepatotoxicity or severe fluid retention), imatinib should be withheld until the event has resolved. Thereafter, treatment can be resumed as appropriate depending on the initial severity of the event.

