5.2 Exclusion Criteria

The subject must be excluded from participating in the trial if the subject:

- Is currently participating and receiving study therapy or has participated in a study of an investigational agent and received study therapy, or herbal/complementary oral or IV medicine, within 2 weeks of the first dose of treatment.
- All toxicities attributed to prior anti-cancer therapy other than alopecia and fatigue must have resolved to Grade 1 (NCI CTCAE v4.0) or baseline prior to administration of first dose of study drug. Subjects with toxicities attributed to prior anti-cancer therapy that are not expected to resolve and result in long-lasting sequalae, such as chronic neuropathy after platinum-based therapy, are permitted to enroll.

- Has received chemotherapy or radiotherapy within 14 days of first dose of study medication.
- Has a solid organ or hematologic transplant.
- Has experienced weight loss >10% over 2 months prior to first dose of study therapy.
- Has a diagnosed additional malignancy within 2 years prior to first dose of trial treatment with the exception of curatively treated basal cell carcinoma of the skin, squamous cell carcinoma of the skin or curatively resected in situ breast cancers. Subjects with another malignancy diagnosed >2 years prior to the first dose of trial medication who were treated with curative intent and are not undergoing active therapy will be eligible.
- Has an active infection requiring systemic therapy.
- Has clinically relevant ascites (defined as requiring paracentesis within 21 days of first dose of study drug) or with moderate radiographic ascites. A minimal amount of radiographic ascites is allowed.
- Has a history or current evidence of any condition, therapy, or laboratory abnormality that might confound the results of the trial, interfere with the subject's participation for the full duration of the trial, or is not in the best interest of the subject to participate, in the opinion of the investigator, including dialysis.
- Has a known psychiatric or substance abuse disorders that would interfere with cooperation with the requirements of the trial.
- Is pregnant or breastfeeding, or expecting to conceive or father children within the projected duration of the trial, starting with the screening visit through 120 days after the last dose of trial treatment.

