8.1.2 Serious Adverse Event

Adverse events are classified as serious or non-serious. A serious adverse event (SAE) is any AE that is:

- Fatal
- Life-threatening
- Requires inpatient hospitalization/prolongation of existing hospitalization, unless:
 - Routine treatment or monitoring of the studied indication, not associated with any deterioration in condiction (procedures such as central line placements, paracentesis, pain control)
 - Elective or pre-planned treatment for a pre-existing condition that is unrelated to the indication under study and has not worsened since the start of study drug
 - Treatment on an emergency outpatient basis for an event not fulfilling any of the definitions of an SAE given above/below and not resulting in hospital administrations
 - Social reasons and respite care in the absence of any deterioration in the patient's general condition
- Results in persistent or significant disability or incapacity
- A congenital anomaly or birth defect
- An important medical event

Important medical events are those that may not be immediately life threatening, but are clearly of major clinical significance. They may jeopardize the subject, and may require intervention to prevent one of the other serious outcomes noted above. For example, drug overdose or abuse, a seizure that did not result in in-patient hospitalization or intensive treatment of bronchospasm in an emergency department would typically be considered serious.

All adverse events that do not meet any of the criteria for serious events should be regarded as non-serious adverse events.

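### Section 8.2.5 sets no worsening limit when it exempts admissions for procedures on a pre-existing condition, which conflicts with 8.2.1 and 8.1.2, so some AEs and SAEs can go unreported

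*Combined protocol and SAP*

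**What the plan says.** Section 8.2.5 opens with two general rules. An AE that leads to admission is reported as serious unless the protocol instructs otherwise, and a condition that leads to surgery is an AE if it fits the AE definition. A list of exemptions follows, introduced by "Neither the condition, hospitalization, prolonged hospitalization, nor surgery are reported as an adverse event in the following circumstances". The first item is "Hospitalization or prolonged hospitalization for diagnostic or elective surgical procedures for a preexisting condition". The third item concerns admissions for treating the target disease and carries its own limit: "unless it is a worsening or increase in frequency of hospital admissions as judged by the clinical investigator". The first item has no such limit.

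Two other sections cover the same ground:

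- Section 8.2.1, for changes while on study: "A preexisting condition should be recorded as an adverse event if the frequency, intensity, or if the character of the condition worsens".
- Section 8.1.2 treats an admission as a criterion of seriousness, with exceptions. The exception for elective or planned treatment applies only to a "pre-existing condition that is unrelated to the indication under study and has not worsened since the start of study drug".

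These rules feed the incidence of Grade 3/4 AEs (a secondary endpoint, Section 2.2.2), the AE and SAE summaries in Section 10.7.5, and the 24-hour SAE reports to the ruxolitinib manufacturer (8.5.2) and to the DSMC (8.5.4).

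**The concern.** A pre-existing condition that gets worse after study drug starts is one of the ways in which a drug effect can show itself, and the protocol says in 8.2.1 that it counts. Section 8.2.5 appears to take it out again whenever the worsening is handled through an admission for elective surgery or a diagnostic procedure. The lead-in removes the condition as well as the admission. A coordinator following that list would therefore record nothing, and one following 8.2.1 and 8.1.2 would report an SAE.

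Two things are at stake: consistency of reporting between subjects, and the direction of any error. The exemption can only remove events. A literal application would make the safety description look more favourable and could stop an expedited report from being sent.

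**Working it through.** The plan gives no figure on this point, so there is nothing to reproduce and no arithmetic applies. The check is to take defined cases through the three rules.

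**Case A: a baseline condition worsens after study drug starts, and the subject is admitted for elective surgery or a diagnostic procedure for it.** Assume that no other 8.1.2 exception applies (routine care of the studied cancer without deterioration, emergency outpatient care, social or respite admission).

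| Rule | Test it applies | Result |
|---|---|---|
| 8.2.1 | Has the condition worsened in frequency, intensity or character? Yes. | AE |
| 8.1.2 | Admitted? Yes. Does the elective exception apply? No, because the condition has worsened. | SAE |
| 8.2.5, first item | Admitted for such a procedure on a pre-existing condition? Yes. | Neither condition nor admission reported |

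The third result is incompatible with the first two.

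**Case B: the same admission, but the condition has not worsened.** Under 8.2.1 the condition is not an AE. Section 8.1.2 defines an SAE as a kind of AE, so with no AE on other grounds the question of seriousness does not arise. Section 8.2.5 says not to report. The rules agree.

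Cases A and B differ only in whether the condition has worsened, so the missing worsening limit is what produces the conflict.

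**Can the text settle Case A by itself?** Three features of 8.2.5 stand in the way:

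1. The third item of the list contains a worsening limit. Its absence from the first item can therefore be read as intended.
2. The opening rule on hospitalized AEs yields to contrary instructions elsewhere in the protocol. The exemption list can be taken as such an instruction.
3. The lead-in names the condition itself, so the list reaches AE status as well as seriousness.

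**Size.** The events at risk are pre-existing conditions that worsen on study and also lead to such an admission. The documents give neither the number of these admissions nor a rate from which to derive it.

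**The case against.** The strongest reply is that the rules can be read together. Section 8.2.1 would decide whether a worsened condition is an AE, and the first item of 8.2.5 would cover only baseline conditions that are not AEs. Other text supports this. The second sentence of 8.2.5 keeps a condition leading to surgery as an AE if it meets the criteria, and Section 8.4 requires every AE in the study period to be recorded. The item might also be read as covering surgical procedures only, so that a purely diagnostic admission falls outside it. The DSMC monitors every treated subject for toxicity (11.3), and the compliance coordinator checks that toxicities have been reported (11.4). Safety is descriptive here, and Section 2.2.2 says that drug-specific safety endpoints will not be assessed.

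Much of this stands. It makes the loss of events conditional and limits its consequences. It does not remove the conflict: the harmonizing reading has to supply a limit that the first item lacks and the third item has, and monitors check against the same conflicting text.

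A reader might infer more than the documents support:

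- **That on-study deteriorations in general drop out of the counts.** Only worsened pre-existing conditions with this kind of admission are affected, and only if 8.2.5 is followed literally.
- **That 8.1.2 contradicts itself by giving "procedures such as central line placements, paracentesis, pain control" as examples of routine care, when Section 5.2 excludes subjects with recent paracentesis or moderate ascites.** The requirement in 8.1.2 that there be no deterioration still governs the examples, so an admission that reflects deterioration is not exempt. Section 8.1.2 also decides only seriousness, so the ascites could still be an AE.
- **That worsening anemia would be lost.** Section 8.2.4 separately makes a laboratory abnormality an AE when it needs active management, including further diagnostic work, and 10.7.5 analyzes laboratory changes.

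**Conclusion.** The point holds as an internal conflict in the reporting rules. For a pre-existing condition that worsens on study and leads to an admission for elective surgery or a diagnostic procedure, 8.2.5 taken literally says not to report, 8.2.1 says AE, and 8.1.2 gives no elective exemption from SAE status. Such events can be left out of the AE and SAE counts, and any error from this source runs toward under-counting.

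The conclusion assumes that at least some staff would apply the 8.2.5 list as written. The size is unknown. It is tempting to express it as one subject divided by the number treated, but that figure would be the same for any missed event and says nothing about how often this one occurs. The effect is confined to the secondary safety endpoint and SAE reporting. The co-primary endpoints and the sample size are not touched.

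**What to change.** Make two wording changes in Section 8.2.5:

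1. Limit the first item to a pre-existing condition that has not worsened since study drug was started, matching the limit already in 8.1.2.
2. State that 8.2.1 decides whether the condition itself is an AE, whatever the reason for the admission.

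Do not also carry over the requirement in 8.1.2 that the condition be unrelated to the indication. That would withdraw the exemption that the first item gives to an admission for the protocol's own tumor biopsies, since the second item covers only efficacy measurement. The worsening limit alone resolves Case A.

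One residual detail: an admission for the optional biopsy at progression (9.4.6) concerns a tumor that has by then worsened. If the sponsor wants that admission to stay exempt, a short clause naming protocol-specified biopsies would do it.

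The cost is protocol wording, with possibly a few more AE and SAE reports. No design, sample size or analysis changes.
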